
Secondary
	
To reduce the rate of all infections after colorectal surgery.
 
To reduce antimicrobial consumption after colorectal surgery
 
To reduce length of hospital stay after colorectal surgery
 
To reduce mortality after colorectal surgery
 
To reduce anastomotic leakage after colorectal surgery
 
To improve quality of life after colorectal surgery
 
To reduce the cost of healthcare treatment associated with colorectal surgery
 
To investigate if pre-operative antibiotic resistance, as determined by antibiotic susceptibility testing of rectally colonising Enterobacteriaceae, is predictive of a patients risk of a post-operative surgical site infection.
 
To investigate the exposure-response relationship for antibiotic prophylaxis in the prevention of surgical site infection prevention after colorectal surgery.
	
All infections within 30 days of operation.
 
Antimicrobial consumption within 30 days of operation.
 
Length of hospital stay after operation
 
Mortality after operation at one year.
 
Radiological or clinically diagnosed anastomotic leakage
 
Quality of life scores pre-operatively and post operatively at 30 days.
 
Cost of healthcare treatments after operation at 30 days.
 
See Table 5
 
See Table 5

Medicinal Product	Cefuroxime 1.5g powder for solution for injection or infusion
Formulation, Dose, Route of Administration	
Formulation
 
Cefuroxime: Each vial contains, as the active ingredient, cefuroxime sodium for injection 1578mg equivalent to 1500mg of cefuroxime respectively
 
Dose
 
Standard treatment
 
 
• 1.5 grams 4 hourly.
 
 
Intervention treatment:
 
 
• A maximum loading dose of cefuroxime 2332 mg
 
• A maximum hourly dose on continuous infusion of 1226 mg/hour. These doses will be administered for a maximum of 6 hours.
 
 
Route of administration
 
Intravenous

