### 1 BACKGROUND

#### Review of published literature

##### **Surgical site infection (SSI) following colorectal surgery**

20,000 patients annually undergo elective colorectal surgery in England with approximately 22% developing a surgical site infection (SSI). SSIs after colorectal surgery have been associated with a 4.6% increase in 30 day mortality, increase hospital stay and cost £5000 per SSI (Jenks 2014).

Colorectal surgery is a common surgical procedure for conditions such as colonic cancer, ulcerative colitis and Crohn's disease. Following surgery, patients undergoing colorectal surgery have a high rate of surgical site infection (SSI), higher than all other types of surgery (Health Protection Agency 2014). SSIs include infections of the site site which encompasses infection of the skin and/or deep tissues (superficial and deep SSIs, as well as infections within the abdomen (organ space SSIs). For the purposes of this study we will refer to superficial and deep SSIs as SSIs (i.e. excluding organ space SSIs). Post operative SSIs in colorectal patients are associated with increased length of hospital stay, increased health care costs (£5000 per SSI) and in the case of organ space SSIs, are associated with an increase in post operative mortality (Coello, 2005, Kirby 2015a).

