##### **Antibiotic prophylaxis to prevent SSI – current practice and limitations.**

In an attempt to prevent SSIs antibiotics are usually given just before an operation, this is called antibiotic prophylaxis. Antibiotic prophylaxis is effective. When initially introduced antibiotic prophylaxis reduced SSI rates from 40% to 10% (Nelson 2014). Currently, published evidence suggests SSI rates after elective colorectal surgery occur in over > 10% of patients (Kirby 2015a, Petrosillo 2008, Smith 2004, Tanner 2009, Wick 2008). The reasons for the higher rate of SSIs now are unclear, but it may represent different definitions (SSI includes organ space infections, SSI does not), more aggressive treatment e.g. pre-operative radiotherapy, or that antibiotic prophylaxis is less effective. In patients undergoing emergency procedures SSI rates are higher than for elective procedures (Morikane 2014). Most SSIs (90%) occur within 14 days of the operation (Kirby 2015a). These infections are commonly caused by bacteria that live in the human bowel. The types of bacteria from the bowel which are believed to cause SSIs are called Enterobacteriaceae, commonly referred to as “coliforms” (e.g. *E. coli*) and anaerobes.

Antibiotic prophylaxis is currently prescribed to patients at doses similar to those used to treat infections such as pneumonia. It is not known if these are the best doses to prevent infections after colorectal surgery. There has only been one study which compared different antibiotic doses for the

prevention of SSI after colorectal surgery. In this study two different-dosing regimens were compared (Gentamicin: 4.5mg/kg and 1.5 mg/kg) in 146 patients. The study determined that the higher dose regimen had a lower SSI rate (22%) than the low dose regimen (55%) (Zelenitsky 2000). Unfortunately other studies have not been completed to further investigate if new, non-treatment based dosing regimens, are better at preventing post-operative SSIs when compared to dosing used for the treatment of infections.

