#### 3.5 Secondary endpoints/outcomes

- All in-patient infections within 30 days of operation
- All in-patient antimicrobial consumption within 30 days of operation.
- Length of hospital stay after operation
- Mortality after operation at one year.
- Anastomotic leak within 30 days of operation
- Quality of life scores pre-operatively and at 30 days.
- Cost of healthcare treatments after operation at 30 days.

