### 10.3.3 Secondary outcome analysis

Secondary outcomes will be analysed by comparing proportions.

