### 10.7 Subject population

Any subject randomised into the study that received at least one dose of study drug will be subjected to the study analysis.

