### 10.8 Procedure(s) to account for missing or spurious data

Strategies to maximise follow-up will be employed including telephone follow up and postal follow up  
No strategies are being planned for missing data.

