### 10.9 Other statistical considerations.

None

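### Length of stay has no time window and no rule for death or readmission, and its only stated analysis does not fit a duration; read plainly, an in-hospital death counts as a short stay

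*Combined protocol and SAP*

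**What the plan says.** The Trial Summary sets the aim as "To reduce length of hospital stay after colorectal surgery", and section 3.2 repeats it, so a shorter stay is read as benefit. Section 3.5 gives the endpoint as "Length of hospital stay after operation" and nothing more. It is the only endpoint in that list without a time point: infections, antimicrobial use, leak, quality of life and cost refer to 30 days, and mortality to one year.

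On who is analysed, section 10.7 says: "Any subject randomised into the study that received at least one dose of study drug will be subjected to the study analysis". On method, section 10.3.3 says: "Secondary outcomes will be analysed by comparing proportions". The places where a rule for death could sit do not contain one. Section 10.8 says "No strategies are being planned for missing data", and section 10.9, headed "Other statistical considerations", has no content beyond stating that there are none.

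On data, section 11.1 lists length of stay as one item of the post-operative history form and names no readmission item. The Visit 5 contact in section 7.7 covers outpatient infection, antibiotics and quality of life, but not readmission. The Appendix 4 schedule does include a review of clinical notes at 30 days.

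**The concern.** Stay in days is cut short by death. With no rule, the natural count for a patient who dies on day 3 is 3, which beats a patient who goes home well on day 6. The arm with more early deaths then gains on this endpoint. Mortality is reported separately, at one year, and is not combined with stay.

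Readmission is the second gap. The Background says "Most SSIs (90%) occur within 14 days of the operation", and Visit 5 asks about infections after discharge, so the plan expects some to appear once patients are home. If stay stops at first discharge, any hospital days those infections cause are not counted, although the Background gives longer stay as one of the harms of infection ("SSIs after colorectal surgery have been associated with a 4.6% increase in 30 day mortality, increase hospital stay").

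The third gap is the method. Comparing proportions needs a cut-off, and none is given. The window, the death rule, the readmission rule and the cut-off could all be settled after the data are seen.

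**Working it through.** The plan states no figure for length of stay, so there is none to reproduce. The checks use these inputs.

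- From the documents: 90 patients (10.1) at 1:1 (7.3), so about 45 per arm; infection rates of 16.5% and 8.25% (10.1); a 4.6% excess in 30-day mortality with infection, taken here as percentage points (Background); 90% of infections by day 14 (Background).
- Assumed, because the documents give no figure: a stay of 8 to 20 days had the patient not died; death on days 2 to 5; 5 to 10 hospital days per infection or readmission; 10% to 50% of infections readmitted.

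**Three example records, counted in days**

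| Patient | Course | To first discharge or death | All hospital days |
|---|---|---|---|
| A | Home on day 6 | 6 | 6 |
| B | Dies in hospital on day 3 | 3 | 3 |
| C | Home on day 6, readmitted days 10 to 20 | 6 | 6 + 10 = 16 |

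B ranks best on either count. C equals A on one count and not on the other, and section 3.5 does not say which applies. A proportion does not remove the problem: B falls on the favourable side of any cut-off above 3 days, and each such death is 1/45 = 2.2 percentage points of an arm.

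**Effect of death on an arm mean.** The drop from k deaths is k × (expected stay − day of death)/45.

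- One death, smallest: (8 − 5)/45 = 0.07 days.
- One death, largest: (20 − 2)/45 = 0.40 days.
- Three deaths: 0.2 to 1.2 days.

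**Infection-related excess deaths expected.**

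- Control: 45 × 0.165 × 0.046 = 0.34.
- Intervention: 45 × 0.0825 × 0.046 = 0.17.

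**Benefit being looked for, for scale.** (0.165 − 0.0825) × 5 to 10 days = 0.41 to 0.83 days.

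**Readmission days lost if stay ends at first discharge.** The difference hidden is 0.0825 × share readmitted × days.

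- Smallest: 0.0825 × 0.10 × 5 = 0.04 days.
- Largest: 0.0825 × 0.50 × 10 = 0.41 days.

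With exponential timing (an assumption), the rate is ln(10)/14 = 0.1645 per day, so 44%, 32% and 19% of infections start after days 5, 7 and 10. These are shares of infections, not of readmissions.

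**Simulation, for direction only.** Assumptions: 45 per arm, log-normal stay with median 8 days and log-SD 0.6, deaths on days 1 to 5, 25% of infections readmitted for 7 days and adding no other days. Differences are intervention minus control.

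| Scenario | Plain stay | Death scored 30 days, readmissions added |
|---|---|---|
| Mortality 2% (control) v 6% (intervention), equal infection rates | −0.28 | +0.81 |
| Intervention doubles infections, equal mortality | about 0.0 | +0.28 |

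Deaths reverse the sign. Lost readmission days only pull the difference towards zero.

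**The case against.** The strongest reply is that the plan sets no scoring rule at all. A reader might infer that it scores death as a short stay and gives readmission no days. It says neither, and the wording of the endpoint could include readmission days. That stands: the defect is an undefined endpoint, and the adverse scoring is what the ordinary reading would produce.

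A reader might also infer that one death can cancel the whole expected benefit. Scoring a day-3 death as 3 rather than 30 moves an arm mean by (30 − 3)/45 = 0.6 days, but the 30 is a penalty that appears nowhere in the plan. Against the stay the patient would otherwise have had, the shift is 0.07 to 0.40 days, below the assumed benefit of 0.41 to 0.83. Section 10.3.3 does not prescribe a comparison of means either.

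The link from infection to death is weaker than the 4.6% suggests. The same Background section excludes organ space infections from the trial's definition and ties raised mortality to that type, so the 0.34 and 0.17 excess deaths are probably too high. Deaths from other causes still enter the endpoint.

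Nor is every dosed patient certain to contribute. Section 7.2 stops data collection after loss of capacity, and section 9.7 withdraws overdosed patients. Finally, mortality is reported separately, so a reader could see an imbalance. That helps interpretation but does not define the endpoint.

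**Conclusion.** The point holds as an undefined secondary endpoint paired with an unsuitable method. Sections 3.5, 10.3.3 and 10.7 together do not determine what is counted, until when, or how it is compared. On the ordinary reading in days, in-hospital deaths can favour the arm in which more occur. Ending stay at first discharge would mainly dilute a true difference, by 0.04 to 0.41 days on the assumed ranges. The documents do not support saying that lost readmissions favour the worse arm.

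The size in this pilot is probably modest: about 0.1 to 0.4 days on a 45-patient arm mean per early death, with few deaths expected. This rests on the assumed stay of 8 to 20 days and death on days 2 to 5. The endpoint is secondary and the trial has 90 patients, so this is a cheap improvement and no threat to the primary comparison. It is worth making now because section 10.1 looks ahead to a full study.

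**What to change.** - **Section 3.5:** define the endpoint as total days in hospital from operation to day 30, readmissions included, with any death by day 30 ranked worse than every survivor, including one still in hospital at day 30.
- **Section 10.3.3:** for this endpoint, replace the comparison of proportions with a rank test and a difference in medians. Report deaths by arm and the plain index stay alongside.
- **Data:** take discharge, readmission and death dates from the 30-day notes review in Appendix 4. Add a readmission question to the existing Visit 5 contact, which would also pick up admissions elsewhere, and a matching item on the form in section 11.1.

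The cost is a sentence in each of two sections, one question and one form item, with no new visit. Stays beyond day 30 are capped, and the main figure is no longer the plain index stay, though that is still tabulated.

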#### 3.6 Exploratory endpoints/outcomes

Table 5: Exploratory endpoints		
Objectives	Outcome Measures	Timepoint(s) of evaluation of this outcome measure (if applicable)
To explore the impact of the antibiotic susceptibility of rectally colonising Enterobacteriaceae on the	Minimum Inhibitory Concentration of the Predominant Enterobacteriaceae	Pre-operative

efficacy of antibiotic prophylaxis in patients receiving standard antibiotic dosing, and in patients receiving PD target based dosing.
	
Minimum Inhibitory Concentration of the most resistant Enterobacteriaceae
 
Minimum Inhibitory Concentration of the predominant E. coli.
 
Surgical site infection rate within 30 days of operation
	

To determine exposure response relationships within patients treated with standard antibiotic dosing.
	
Free serum drug levels
 
MICs of colonising Enterobacteriaceae
 
Exposure response relationships including:
 
fT>MIC
 
CMAX/MIC
	
1,2,3 and 4 hours post initiation of antibiotic prophylaxis.

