### 3.2 Secondary objectives

To determine if pharmacodynamic target (4xMIC90 free serum concentrations) based continuous antibiotic dosing of antibiotic prophylaxis reduces the rate of all in-patient infections after colorectal surgery when compared against standard antibiotic prophylaxis dosing regimens.

To determine if pharmacodynamic target (4xMIC90 free serum concentrations) based continuous antibiotic dosing of antibiotic prophylaxis reduces the in-patient consumption of antibiotics after colorectal surgery when compared against standard antibiotic prophylaxis dosing regimens.

To determine if pharmacodynamic target (4xMIC90 free serum concentrations) based continuous antibiotic dosing of antibiotic prophylaxis reduces the length of hospital stay after colorectal surgery when compared against standard antibiotic prophylaxis dosing regimens.

To determine if pharmacodynamic target (4xMIC90 free serum concentrations) based continuous antibiotic dosing of antibiotic prophylaxis reduces mortality after colorectal surgery when compared against standard antibiotic prophylaxis dosing regimens.)

To determine if pharmacodynamic target (4xMIC90 free serum concentrations) based continuous antibiotic dosing of antibiotic prophylaxis reduces anastomotic leak after colorectal surgery when compared against standard antibiotic prophylaxis dosing regimens.

To determine if pharmacodynamic target (4xMIC90 free serum concentrations) based continuous antibiotic dosing of antibiotic prophylaxis improves quality of life after colorectal surgery when compared against standard antibiotic prophylaxis dosing regimens.

To determine if pharmacodynamic target (4xMIC90 free serum concentrations) based continuous antibiotic dosing of antibiotic prophylaxis reduces the cost of healthcare treatment after colorectal surgery when compared against standard antibiotic prophylaxis dosing regimens.

To determine if pre-operative antibiotic resistance, as determined by antibiotic susceptibility testing of rectally colonising Enterobacteriaceae, is predictive of a patients risk of a post-operative surgical site infection.

To determine the exposure-response relationship for antibiotic prophylaxis in the prevention of surgical site infection prevention after colorectal surgery.

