### 7.11 Storage and analysis of samples

Criteria for the collection, analysis, storage and destruction of biological samples

Rectal swab

- Testing location: Old Medical School, Leeds General Infirmary.
- Timings of testing: Pre-operative
- Shipping details: Clinical transport system
- Sample destruction: At the end of the laboratory studies have been completed, not expected to be > 1 year after date of the participant recruitment.
- Sample storage
  - o Conditions: 4 degrees Celsius +/- 5 degrees Celsius
  - o Duration: As sample destruction
  - o Location: as testing location
  - o Long term storage: None
- Laboratory manual: Available in the Old Medical School, Leeds General Infirmary

Blood samples for antibiotic drug concentrations

- Whole blood
- 6 ml
- Blood tube: Serum separator tube
- Testing location: Southmeads antimicrobial reference laboratory.

- Timings of testing: 4 samples taken intra-operatively. One sample will be collected at approximately 10 minutes after antibiotic infusion. One sample will be collected prior to closing the surgical wound. The other two samples will be taken after the surgery is approximately 1/3rd and 2/3rds complete. If a patient is re-dosed intra-operatively one of these two samples can be moved to be taken prior to the re-dosing.
- Shipping details: On ICE to Southmeads Antibiotic reference laboratory
- Sample destruction: As per Southmeads local guidelines (not more than 7 days of result)
- Sample storage
  - o Conditions: Freezer (-20 or -80 degrees)
  - o Duration: Until testing
  - o Location: Leeds and Southmeads
  - o Long term storage: None

Responsibilities of the trial site in regard to samples: The trial site to ensure that samples are appropriately labelled in accordance with the trial procedures to comply with the 1998 Data Protection Act. Biological samples collected from participants as part of this trial will be transported, stored, accessed and processed in accordance with national legislation relating to the use and storage of human tissue for research purposes and such activities shall at least meet the requirements as set out in the 2004 Human Tissue Act and the 2006 Human Tissue (Scotland) Act.

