# 10 STATISTICS AND DATA ANALYSIS

## 10.1 Sample size calculation

This study is a pilot study intending to recruit 90 patients. We require 60 patients with blood samples collected for pharmacokinetic analysis. In approximately 30% of patients it is not possible to obtain blood samples for intra-operative technical reasons.

The full study sample size will be based on the following data:

- Alternative hypothesis: Pharmacodynamic target (4xMIC90 free serum concentrations) based continuous antibiotic dosing of antibiotic prophylaxis reduces the rate of surgical site infection after colorectal surgery by 50% when compared against standard antibiotic prophylaxis dosing regimes.

Justification: Ceftriaxone reduces surgical site infection in colorectal surgery by 39% compared to other cephalosporin regimes (odds ratio 0.61). It is believed this benefit is achieved by obtaining optimal PD targets. The PD target approach to antibiotic prophylaxis investigated in this study is attempting to obtain an equivalent benefit seen from ceftriaxone, without using ceftriaxone. We expect this 39% benefit to be restricted to patients who have operations over 2 hours. As 73% of patients have operations over 2 hours we expect the reduction in SSIs to be 53% (39/73).

Treatment Effect or Alternative Hypothesis: is this the smallest size of effect that would be of clinical interest- how is this justified in the form of appropriate references, pilot data or clinical arguments.

- Null Hypothesis: Pharmacodynamic target (4xMIC90 free serum concentrations) based continuous antibiotic dosing of antibiotic prophylaxis does not reduce the rate of surgical site infection after colorectal surgery when compared against standard antibiotic prophylaxis dosing regimes i.e. there is an absolute difference in response rates between arms of zero.
- Significance level: 0.05.
- Power: 90%
- Adjustments to sample size based on interim analysis(es)
- SSI rate in standard treatment group (operations > 2 hours)
  - 16.5% (estimated from elective patients only)
- SSI rate in investigation group: 50% of standard group=8.25%

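### Table 5 limits the exposure-response analysis to the standard arm, which is narrower than the objective it serves and the sampling planned for it

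*Combined protocol and SAP*

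**What the plan says.** The second row of Table 5 (section 3.6) sets this exploratory aim: "To determine exposure response relationships within patients treated with standard antibiotic dosing". Its measures are free serum levels, MICs of colonising Enterobacteriaceae, fT>MIC and CMAX/MIC. The row above it, on isolate susceptibility, names both arms: it concerns the "efficacy of antibiotic prophylaxis in patients receiving standard antibiotic dosing, and in patients receiving PD target based dosing".

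The objective that the second row serves has no arm limit. Section 3.2 has "To determine the exposure-response relationship for antibiotic prophylaxis in the prevention of surgical site infection prevention after colorectal surgery". The Trial Summary has "To investigate the exposure-response relationship for antibiotic prophylaxis in the prevention of surgical site infection prevention after colorectal surgery" and sends the reader to Table 5 for the outcome measure.

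Section 10 gives no exposure-response analysis. Sections 10.3.2 and 10.3.3 only compare proportions, and section 10.4 plans no subgroups. Table 5 is therefore the only place that fixes the population.

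Section 7.11 plans "4 samples taken intra-operatively" without reference to arm. Section 10.1 says: "This study is a pilot study intending to recruit 90 patients", "We require 60 patients with blood samples collected for pharmacokinetic analysis" and "In approximately 30% of patients it is not possible to obtain blood samples for intra-operative technical reasons".

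**The concern.** The Background says that the exposure-response relationship for prophylaxis is unknown and gives that gap as the reason for the study. Yet the one analysis aimed at it is confined to the arm that is not designed to hold levels at the target. Because the adjacent row names both arms, the limit is hard to read as shorthand for all patients.

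Two things are at stake. The first is information: patients and events already measured are not used for this question. The second is interpretation. Within the standard arm, fT>MIC varies largely with the isolate's MIC and with patient factors such as renal function, none of them randomised. Between the arms, exposure differs by random allocation. An analysis of the standard arm alone has no access to that contrast, and it cannot describe SSI occurrence under sustained exposure near the target.

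**Working it through.** **Inputs.** 90 patients, 60 to be sampled, about 30% not obtainable, SSI rates of 16.5% and 8.25% (all section 10.1); 1:1 simple randomisation (section 7.3); isolates cultured in 55 of 63 patients, MIC distribution and estimated free levels (section 1, including Tables 1 and 2); free target of 64 mg/L (section 1, description of the proposed study).

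**1. The plan's own figures.** 60/(1 − 0.30) = 85.7, so 86 patients; in reverse, 90 × 0.70 = 63. A one-third loss gives exactly 90. The 90 therefore looks like cautious rounding of an approximate 30%, not an error. The infusion rate reproduces: 0.5 × 16.5% = 8.25%.

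**2. Are both arms needed for 60?** One arm of 45 gives 45 × 0.70 = 31.5 sampled patients. Sixty can be reached only by sampling both arms.

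**3. Patients and events left out (equal arms).**
- 63 sampled: 31.5 × 0.165 = 5.2 SSIs in the standard arm and 31.5 × 0.0825 = 2.6 in the infusion arm, 7.8 in all.
- 60 sampled: 30 × 0.165 = 4.95 and 30 × 0.0825 = 2.48, 7.4 in all.
- Share of SSIs left out: 8.25/(16.5 + 8.25) = 33.3%, whatever the sample size. Share of measured patients left out: one half.
- With 30 per arm, the binomial chance of four or fewer SSIs is 43% for the standard arm alone and 12% for both arms.

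**4. Sensitivity of the one-third.** Share = p2/(p1 + p2) with p1 = 16.5%; for an odds ratio, p2 = p1·OR/(1 − p1 + p1·OR).

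| Assumed effect | p2 | Share left out |
|---|---|---|
| 53% reduction (39/73, section 10.1) | 7.68% | 31.8% |
| 50% reduction (planned) | 8.25% | 33.3% |
| OR 0.50 (Background) | 8.99% | 35.3% |
| 39% reduction | 10.07% | 37.9% |
| OR 0.61 (section 10.1) | 10.76% | 39.5% |
| No effect | 16.5% | 50% |

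Simple randomisation need not give equal arms. If the 60 split 38 standard to 22 infusion, the share is 22%; if 22 to 38, it is 46%.

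**5. Patients without an isolate.** Both metrics need an MIC. At 55/63 = 87.3% with a cultured isolate, 5.2 becomes about 4.5 and 7.8 becomes about 6.8.

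**6. Exposure range.** Table 2 estimates free levels after 1.5 g of 21.5, 12.15, 7.8 and 4 mg/L at 1 to 4 hours. Against 64 mg/L these are 34%, 19%, 12% and 6%, so the target is not sustained. On fT>MIC the picture depends on the isolate:
- MIC 4 or below (7.3 + 70.9 = 78.2% of those cultured): 21.5/4 = 5.4 × MIC at 1 hour and 4/4 = 1 × MIC at 4 hours, so fT>MIC is near its ceiling under standard dosing.
- MIC 16 (7.3%): the level falls below the MIC between 1 and 2 hours.
- MIC 32 or above (10.9%): it is already below at 1 hour.

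The arms should therefore separate on fT>MIC mainly in the 18.2% with MIC 16 or above. That is about 31.5 × 10/63 = 5 patients per arm.

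**The case against.** The case for leaving the row alone is a fair one. It is exploratory, and whether low levels under current dosing go with SSI is a sensible question that follows from the Background. A within-arm analysis is also not driven by other differences between the regimens. The gain from pooling is only about 2.5 SSIs, and those counts apply rates estimated from elective patients to a pilot that also takes emergencies. All of this stands. It argues for keeping the standard-arm analysis and for modest claims, but not for leaving the infusion arm out.

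A reader might infer more than the documents support:

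- **That standard dosing never reaches the target.** Section 2.1 says that 64 mg/L is exceeded after a bolus (free or total is not stated), and section 7.11 takes a sample at about 10 minutes. Only sustained exposure is missing.
- **That the standard arm covers only a narrow, low range.** On fT>MIC, step 6 shows that it already spans much of the range because MICs vary. Most infusion patients would sit near the ceiling.
- **That the infusion arm supplies higher peaks.** In Table 7, loading doses up to the 80–90 kg band are 617 to 1499 mg, below the 1.5 g bolus; only the two heaviest bands exceed it (1675 and 1851 mg). The stated maximum of 2332 mg differs from Table 7, and those passages must be reconciled. A higher CMAX is not shown.
- **That infusion-arm levels are thrown away.** They still count towards the 60 for pharmacokinetic analysis. The omission concerns this row only.
- **That the trial cannot test its premise.** Whether targeting 4×MIC90 reduces SSI is the randomised primary comparison, which uses both arms.

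**Conclusion.** The point holds as an inconsistency with a modest analytic cost. Table 5 is narrower than the objective in section 3.2 and the Trial Summary, and narrower than the sampling in sections 7.11 and 10.1. In this analysis it omits about half the measured patients and, at the planning rates with equal arms, about a third of expected SSIs (about 5 analysed instead of 7 to 8, or about 4.5 instead of 6.8 after allowing for missing isolates). With equal arms the share ranges from about 32% to 50% over the effects considered. It also omits the arm designed to sustain free levels near 64 mg/L and the randomised contrast in exposure.

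The size rests on full-study planning rates, the 30% sampling loss being the same in both arms, and the feasibility study's culture rate carrying over. Adding the infusion arm improves the analysis but does not make it adequate for modelling: 7 to 8 events support description only. The primary comparison is unaffected, so this is a minor point.

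**What to change.** Reconcile the Trial Summary, section 3.2 and Table 5 by rewording the exposure-response row to cover all sampled patients in both arms who have an available MIC. Then:

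- Summarise SSI by individual fT>MIC and by CMAX/MIC, overall and separately by arm.
- Keep the within-standard-arm analysis alongside.
- Report attainment of the free-concentration target by arm.
- Label the whole analysis descriptive and exploratory, giving the expected number of SSIs (about 7 to 8 before allowing for missing isolates) as the reason.
- State that the pooled summary partly reflects the between-arm difference, which is why the by-arm results are shown with it.

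The cost is a one-row edit and a small amount of extra analysis. No additional patients, samples or visits are needed, and nothing about treatment changes.
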